TKI258 500mg PO daily for 5 days, followed by a 2 day rest period. Each cycle is 28 days.

Duration of Treatment:

Patients will continue to receive TKI 258 until progression, unacceptable toxicity or withdrawal of consent

Statistical Methods:

This is a phase IIA activity trial of TKI 258 for treatment of castrate resistant prostate cancer with skeletal metastases. The two primary outcomes are survival time and early response as characterized by a drop in PSA as defined by Prostate Cancer Working Group 2 criteria. Based on a historical mean survival of time 8 months, a mean survival time on average > 10 months with TKI258 would be considered promising evidence of anti-disease activity. The planned sample size is 40 patients, with an anticipated accrual rate of 3

patients per month. Based on historical experience using carefully selected candidates with evidence for iliac involvement on bone scan, we anticipate that ~60% of patients will have positive biopsies. No early stopping rule in terms of the probability of PSA response will be employed because blocking the stromal-epithelial interactive pathway (SE-pathway) may produce clinical benefit independent of PSA modulation. Consequently, it may be the case that TKI258 does not cause significant reductions in PSA, but survival time is prolonged due to inhibition of disease progression. Given the short survival time of these patients and anticipated accrual rate of 3 patients per month, it also will not be feasible to implement an early stopping rule in terms of observed survival times. Based on an historical rate of 20% grade 3 or 4 toxicity with standard therapies the method of Thall and Sung (1998) will be used to monitor toxicity.

Unadjusted survival time will be estimated using the method of Kaplan and Meier (1958) and the effects of the following four potential prognostic covariates Inhibition of FGF signaling by bone marrow biopsy at 8 weeks, modulation of the bone markers (a) urinary NTX and (b) bone specific alkaline phosphatase, and baseline signature of FGF signaling in terms of FGF R-1, FGF R-3 and FGF 9 on Prob(PSA response) will be estimated using logistic regression, and on survival time will be estimated using the Cox model or an appropriate time-to-event regression model.

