7.4 Evaluation during Treatment

On-study tests/visits that must occur within a defined time frame will have a standing window of allowance that is equal to +/- 3 days for any laboratory testing. If

screening lab tests take place less than 7 days prior to C1D1, laboratory testing will not be repeated.

7.4.1 Beginning on Cycle 1 Day 1 and continuing every 4 weeks thereafter, patients will undergo the following additional testing:

- History and physical exam
- Vital Signs (BP, pulse)
- Weight
- PS (ECOG)
- Assessment of concurrent medications
- Assessment of AEs
- PSA test
- Blood for Biomarker studies (Day 1 of Cycles 2 and 3 only)
- Serum chemistry must include: BUN, creatinine, total bilirubin, albumin, SGOT [AST], SGPT [ALT], GGT, LDH, amylase, lipase, alkaline phosphatase, fasting glucose, calcium, sodium, magnesium, phosphorus, and potassium

7.4.2 On Cycle 1, Days 12 and 26 and Cycle 2 Day 12 patients will undergo the following tests:

- CBC with differential/platelets
- Serum chemistry must include: BUN, creatinine, total bilirubin, albumin, SGOT [AST], SGPT [ALT], GGT, LDH, amylase, lipase, alkaline phosphatase, fasting glucose, calcium, sodium, magnesium, phosphorus, and potassium
- There will be a blood draw for a TKI258 trough concentration (Cycle 2 Day 12 Only) to evaluate the potential relationship of safety and efficacy in regards to steady state drug concentrations.

Note that the Day 26 of Cycle 1 visit could end up being scheduled on the same day as the Day 1 of Cycle 2 visit described above.

7.4.3 Beginning on Cycle 1 Day 1 and every 4 weeks for the first 8 weeks, and every 8 weeks thereafter, patients will undergo the following additional testing:

- Urine N-telopeptide
- Bone Alkaline Phosphatase

7.4.4 ECGs, cardiac enzymes, and MUGA/ECHO during therapy will be assessed as shown below in Table 7.1:

Table	7.1
-------	-----

Assessment	Cycle and Day	Time Point
12-lead ECG	Screening	Anytime
	Cycle 1, Day 1	3 sequential ECGs, separated
		by at least 5 to 10 minute
		intervals pre-dose
	Cycle 1, Day 1	1 ECG six hours post-dose
	Cycle 1, Day 26	1 ECG pre-dose
	Cycle 2, Day 26	1 ECG pre-dose
	Cycle 3, Day 26	1 ECG pre-dose
	Cycle 4+, Day 1	Anytime at the end of the
		previous cycle
	EOT	Anytime
Cardiac enzymes (troponin I	Screening	Anytime to coincide with
or B, CPK, and CPK-MB)		ECHO/MUGA
	Every 12 weeks while	To coincide with
	receiving therapy	ECHO/MUGA
	EOT	Anytime to coincide with
		ECHO/MUGA

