ECHO/MUGA	Screening	Anytime to coincide with
		cardiac enzymes
	Every 12 weeks while	To coincide with cardiac
	receiving therapy	enzymes
	ЕОТ	Anytime to coincide with
		cardiac enzymes.

7.4.5 A bone marrow biopsy and aspirate will be performed between 7 and 10 weeks (preferably at week 8) after beginning treatment. The specimens will be evaluated by pathology. A small portion of the bone marrow aspirate will be used for bone marker testing (to include bone marrow androgen levels).

7.4.6 Routine restaging scans and/or other disease assessment diagnostics will be performed every 8 weeks for the first 6 months and every three months thereafter. Such studies can be also be performed at the time of clinical disease progression (at the discretion of the study investigator).

7.5 Final Study Visit:

At the end of the study and within 4 weeks of study drug termination the following will be performed

- History and physical exam
- Vital Signs (BP, pulse)
- Weight

- Eastern Cooperative Oncology Group (ECOG) Performance Status
- Assessment of concurrent medications
- Adverse event evaluation
- Laboratory testing:
- CBC with differential/platelets
- Serum chemistry must include: BUN, creatinine, total bilirubin, albumin, SGOT [AST], SGPT [ALT], GGT, LDH, amylase, lipase, alkaline phosphatase, fasting glucose, calcium, sodium, magnesium, phosphorus, and potassium
- PSA test
- N-telopeptides in urine
- Correlative Studies (serum and bone marrow androgen testing, plus additional serum/plasma banking)
- Disease Status Assessment
- Chest X-ray
- Electrocardiogram (if not done in the past 6 weeks)
- CT or MRI scans of the pelvis and abdomen (if indicated)
- Bone scan (if indicated)
- Bone marrow biopsy and aspirate: The specimens will be evaluated by pathology. A small portion of the bone marrow aspirate will be used for bone marker testing.
- 7.6 Long-Term Follow Up

Patients will be followed a minimum of every 3 months by clinic visit (at M.D. Anderson or a local physician), telephone or e-mail correspondence to assess delayed toxicity and survival time.

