Data Analysis. If the data on the 40 patients yield a sample mean of 10 months (the targeted 25% improvement) based on total follow-up time 400 months (all 40 deaths observed) then the posterior of m would be IG(42.064, 408.512), which has mean 9.95 months and posterior 95% credible interval 7.33 - 13.4 months. Similarly, if 35 deaths are observed with 5 death times administratively censored and total follow-up 460 months at the final analysis then the posterior of m would be IG(37.064, 468.512),), which has mean 13 months and posterior 95% credible interval 9.39 - 17.95 months. Unadjusted survival time will be estimated using the method of Kaplan and Meier (27). The effects of the following four potential prognostic covariates on Prob(PSA response) will be estimated using logistic regression (28), and on survival time will be estimated using the Cox model or, if the proportional hazards assumption is not satisfied, using an appropriate time-to-event regression model chosen based on preliminary goodness-of-fit analyses of the data (29). Each of the following covariates is a binary indicator.

- 1. Inhibition of FGF signaling by bone marrow biopsy at 4 weeks.
- 2. Modulation of the bone markers (a) urinary NTX and (b) bone specific alkaline phosphatase
- 3. Baseline signature of FGF signaling in temrs of FGF R-1, FGF R-3 and FGF 9.

Time of disease progression if defined by PSA alone is defined as follows: Three consecutive PSA elevations above nadir or baseline are required. Each increment in PSA should be a minimum of 1 ng/ml and at least 2 weeks apart or will not count. The time of PSA progression will be taken as the time of the first of these PSA elevations that represents an increment by at least 25% above the nadir or baseline. Given that increments in PSA do not always represent treatment failure, particularly when novel agents with uncertain effects on PSA levels are being evaluated, clinical and radiological correlation is recommended at the discretion of the treating physician. In patients with PSA progression alone without clinical or radiological evidence of disease progression, continued therapy on study is at the discretion of the treating physician in consultation with the principal investigator.

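### Three on-treatment markers enter the survival model with no landmark, no fixed visit for bone-marker modulation and no rule for unmeasured patients, so immortal-time bias can arise

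*Combined protocol and SAP*

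**What the plan says.** The Data Analysis part of Section 10.0 sends a short list of covariates to a logistic model for PSA response and to a survival regression, where effects "on survival time will be estimated using the Cox model or, if the proportional hazards assumption is not satisfied", another time-to-event model chosen on goodness of fit. On their form it says only "Each of the following covariates is a binary indicator". The list reads:

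- "Inhibition of FGF signaling by bone marrow biopsy at 4 weeks"
- "Modulation of the bone markers (a) urinary NTX and (b) bone specific alkaline phosphatase"
- "Baseline signature of FGF signaling in temrs of FGF R-1, FGF R-3 and FGF 9"

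Counting NTX and BAP separately gives the four covariates mentioned in the text. Only the last is known at treatment start.

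The timing of the marrow marker differs between places. Section 10.0 gives 4 weeks, in its opening paragraph and again in the list. The synopsis (Statistical Methods) has "Inhibition of FGF signaling by bone marrow biopsy at 8 weeks". Section 7.4.5 says "A bone marrow biopsy and aspirate will be performed between 7 and 10 weeks (preferably at week 8) after beginning treatment". Section 7.5 also asks for a marrow sample at the final visit, and the plan does not say whether that sample may be used to classify a patient.

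For NTX and BAP, Section 7.4.3 sets the schedule: "Beginning on Cycle 1 Day 1 and every 4 weeks for the first 8 weeks, and every 8 weeks thereafter". No visit, cut-off or time window defines modulation. Neither the synopsis nor Section 10.0 states a time origin for the regression, a landmark, time-dependent coding, or how to handle a patient without an on-treatment value.

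**The concern.** A patient must live, and usually stay on treatment, long enough to be measured before being classed as inhibited or modulated. If a patient who dies earlier is placed in the negative group, that group collects early deaths that the positive group cannot have. The marker then appears to go with longer survival when there is no link. If a marker is measured repeatedly and counted positive once it has ever changed, patients who live longer get more chances to be positive, with the same result.

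At stake is how the trial would report the relation between on-treatment FGF inhibition or bone-marker change and survival. Survival is one of the two primary outcomes, and this regression is where the plan links the markers to it. The only fallback in the plan concerns proportional hazards, which does not address this problem.

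**Working it through.** **Plan's own figures.** The plan gives none for the marker models. Its survival figures do reproduce. The prior IG(2.064, 8.512) has mean 8.512/(2.064 − 1) = 8.0 months. The posterior IG(42.064, 408.512) has mean 408.512/41.064 = 9.95 months and interval 7.33 to 13.47 (printed 13.4). The 8-month historical mean and 10-month target are used below.

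**Step 1: deaths before the marker visit.** Inputs: N = 40, mean 8 or 10 months (Section 10.0), visit weeks from Sections 7.4 and 10.0. Assumption: exponential survival. With t = 7 × weeks/30.44 months, P(death before t) = 1 − exp(−t/mean).

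| Visit | t (months) | Mean 8 | Deaths of 40 | Mean 10 | Deaths of 40 |
|---|---|---|---|---|---|
| Week 4 | 0.92 | 10.9% | 4.3 | 8.8% | 3.5 |
| Week 8 | 1.84 | 20.5% | 8.2 | 16.8% | 6.7 |
| Week 10 | 2.30 | 25.0% | 10.0 | 20.5% | 8.2 |

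**Step 2: single-visit marker, true hazard ratio 1.** Simulated trials of 40 patients, one-covariate Cox model, two-sided 5% test, marker independent of survival, week-8 visit, mean 8 months. The share positive is not in the documents, so 30% to 70% is shown. Where two figures are given, they span runs under slightly different follow-up assumptions, including one with 3 patients accrued per month and 12 months of follow-up after accrual.

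| Share positive | Unmeasured coded negative: median HR | False positives | Unmeasured dropped: median HR | False positives |
|---|---|---|---|---|
| 30% | 0.72–0.76 | 9–10% | about 1.0 | about 5% |
| 50% | 0.65–0.67 | 22% | about 1.0 | about 5% |
| 70% | 0.53–0.55 | 44–46% | about 1.0 | about 5% |

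With unmeasured patients coded negative, nearly all false positives favour the marker. Over weeks 4 to 10 and means of 8 to 10 months, the HR under that coding runs from 0.48 to 0.87.

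Dropping unmeasured patients gives the same result as a landmark analysis at that visit (HR 0.98 to 1.02, false positives 4.4% to 5.6%). The Cox partial likelihood depends only on the order of deaths and on who is at risk at each one. Subtracting the same death-free period from every retained patient changes neither.

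**Step 3: NTX or BAP counted as modulated at any visit, true hazard ratio 1.** Visits at weeks 4 and 8, then every 8 weeks. Assumptions: 15% to 30% chance of a qualifying change per visit, mean 6 months on treatment, survival mean 8 or 10 months.

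- All patients included: HR about 0.60 to 0.67.
- Never-measured patients dropped: HR about 0.69 to 0.74, false positives about 9% to 17%.

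Dropping unmeasured patients does not remove this bias, because it comes from the number of chances to be classed positive.

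**The case against.** The strongest reply is that the plan never says to code unmeasured patients as negative. A patient who dies before the biopsy has no value for inhibition, and ordinary software drops a missing covariate. For a marker read once, that gives an unbiased hazard ratio among patients who reach the visit. This stands. A reader might infer that the planned Cox model must produce a spurious advantage, or would do so even with visit and cut-off fully defined. The documents do not support either reading. The bias needs a coding rule that the plan leaves open, or a definition of modulation spread over several visits. A fixed covariate and a clock starting at treatment are natural readings too, but neither is written.

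The larger error rates also depend on the share positive. Section 10.0 expects about 60% positive biopsies. If inhibition can be scored only where tumour is present (an assumption, since Section 3.1 also names host cells), half of those inhibited would be 0.6 × 0.5 = 30% of patients, the mildest row in the table. Exponential survival may also overstate early deaths in patients selected for ECOG status of 2 or better.

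A reader might further note that measured patients counted from treatment start would average 8 + 1.84 = 9.8 months, close to the 10-month benchmark, with no drug effect. The arithmetic is right, but the plan calls for no mean survival by marker group, and its decision rule uses unadjusted survival.

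The reply does not settle NTX and BAP. They are measured repeatedly, no visit fixes their status, and an ever-modulated definition stays biased after unmeasured patients are dropped.

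**Conclusion.** The concern holds as a gap in specification that allows immortal-time bias, not as a bias built into the model. Early deaths are frequent enough to matter: about 8 of 40 before week 8 and 10 before week 10 with an 8-month mean, about 7 and 8 with a 10-month mean. Two choices left open would bias the result under no effect. Coding unmeasured patients as negative gives an HR of about 0.53 to 0.76 for a week-8 marker. An any-visit definition of NTX or BAP modulation gives about 0.69 to 0.74 among measured patients. One available choice, a single common visit with unmeasured patients dropped, gives about 1.0, but its result applies only to patients who reach that visit.

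These sizes rest on exponential survival, markers unrelated to survival, the assumed positive shares and visit probabilities, and 6 months' mean treatment. The baseline FGF signature is unaffected. The covariate analysis is described as exploratory and does not enter the Bayesian decision rule. The change should be made, but the primary survival conclusion does not depend on it.

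**What to change.** First reconcile the on-treatment biopsy timing across the synopsis (8 weeks), Section 10.0 (4 weeks, twice) and Section 7.4.5 (weeks 7 to 10). Then add to Section 10.0:

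- Analyse every on-treatment marker from one common landmark at the end of the reconciled biopsy window.
- Include only patients alive and in follow-up at the landmark, and measure survival from it.
- Classify patients by markers obtained up to the landmark, with NTX and BAP modulation tied to a named visit and cut-off. State whether a final-visit marrow sample taken before the landmark counts.
- Never code an unmeasured patient as negative. Report how many were excluded and why (death, loss to follow-up, stopped treatment, no usable sample).
- Alternatively, enter NTX and BAP as time-dependent covariates.
- Keep treatment start as time zero only for the baseline FGF signature, in a separate model.

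The cost is wording in the statistical section, with no new data beyond the scheduled visits. The price is that about 7 to 10 early deaths leave the on-treatment marker models (6.7 at week 8 with a 10-month mean, 10.0 at week 10 with an 8-month mean), so conclusions hold only for patients who reach the landmark.

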2.0 STUDY OBJECTIVES

2.1 Primary Objective

The primary objective of this study is:

- To estimate overall survival and early response as characterized by a drop in PSA
- To identify the PSA modulation in 40 selected patients with advanced prostate cancer, and to correlate PSA Modulation with changes in bone remodeling markers.

Secondary Objectives

The secondary objectives of this study are:

- To estimate the objective tumor response rate for subjects with measurable disease at baseline.
- To explore the potential association between serum PSA and bone turnover markers with bone marrow FGF R 1 and FGF9 while on TKI 258
- To explore the predictive values of baseline FGF R 1, FGF9, and FGF signaling in serum and those in the bone marrow before and during treatment with TKI258
- To identify candidate mRNA gene expression changes in bone marrow biopsy aspirate following treatment with TKI258
- To collect and archive bone marrow biopsies and aspirates, serum and plasma in study patients for later hypothesis generating associations
- To explore FGF R expression following eight weeks of TKI 258.

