4.2 Exclusion Criteria

Patients who meet any of the following criteria will be excluded from the study.

- 1. Histologic variants other than adenocarcinoma in the primary tumor
- 2. Abnormal liver functions consisting of any of the following:
 - a) Serum bilirubin $\ge 1.5 \text{ x ULN}$

b) AST and ALT $> 2.5 \times ULN$

- 3. Therapy with other hormonal therapy, including any dose of Ketoconazole, finasteride (Proscar), dutasteride (Avodart) any herbal product known to decrease PSA levels (eg, Saw Palmetto and PC-SPES) within 4 weeks of study drug.
- 4. Requirement for corticosteroids greater than the equivalent of 7.5 mg of prednisone daily.
- 5. Therapy with samarium or strontium within 8 weeks prior to first dose of study drug.
- 6. Active infection or concomitant illness that is not controlled with medical management.
- 7. Prior radiation therapy completed < 4 weeks or single fraction of palliative radiotherapy within 14 days prior to first dose of study drug.
- 8. Any "currently active" second malignancy, other than non-melanoma skin cancer. Patients are not considered to have a "currently active" malignancy, if they have completed therapy and are considered by their physician to be at least less than 30% risk of relapse over next 3 months.
- 9. Active psychiatric illnesses/social situations that would limit compliance with protocol requirements.
- 10. Active or uncontrolled autoimmune disease that may require corticosteroid therapy during study
- 11. Severely compromised immunological state, including being positive for the human immunodeficiency virus (HIV)
- 12. Acute or chronic hepatitis B or C
- 13. Chemotherapy and other investigational therapies (targeted or immunotherapy) will require a 4-week washout period before treatment initiation
- 14. Initiation of bisphosphonate therapy within 4 weeks prior to first dose of study drug. Patients on stable doses of bisphosphonates that show subsequent tumor progression may continue on this medication; however, patients are not allowed to initiate bisphosphonate therapy during the study.
- 15. Impaired cardiac function or clinically significant cardiac diseases, including any of the following:
 - a. History or presence of serious uncontrolled ventricular arrhythmias or presence of atrial fibrillation
 - b. Clinically significant resting bradycardia (< 50 beats per minute)

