10.0 PLANNED STATISTICAL METHODS

This is a phase IIA activity trial of TKI258 for treatment of castrate resistant prostate cancer with skeletal metastases. The two primary outcomes are survival time and early response as characterized by a drop in PSA as defined by working group criteria. Based on historical mean survival time 8 months, a mean survival time on average > 10 months with TKI258 would be considered promising evidence of anti-disease activity. The planned sample size is 40 patients, with an anticipated accrual rate of 3 patients per month. Based on historical experience using carefully selected candidates with evidence for iliac involvement on bone scan, we anticipate that ~60% of patients will have positive biopsies. No early stopping rule in terms of the probability of PSA response will be employed because it is not known whether blocking the stromal-epithelial interactive pathway (SE-pathway) will be related to clinical benefit. Consequently, it may be the case that PSA does not drop but survival time is prolonged due to inhibition of disease progression by TKI258. Given the short survival time of these patients and anticipated accrual rate of 3 patients per month, it also will not be

feasible to implement an early stopping rule in terms of observed survival times. Based on an historical rate of 20% grade 3 or 4 toxicity with standard therapies the method of Thall and Sung (1998) will be used to monitor toxicity. Unadjusted survival time will be estimated using the method of Kaplan and Meier (1958) and the effects of the following four potential prognostic covariates: Inhibition of FGF signaling by bone marrow biopsy at 4 weeks, modulation of the bone markers (a) urinary NTX and (b) bone specific alkaline phosphatase, and baseline signature of FGF signaling in terms of FGF R-1, FGF R-3 and FGF 9 on Prob(PSA response) will be estimated using logistic regression, and on survival time will be estimated using the Cox model or an appropriate time-to-event regression model.

Preliminaries: This is a phase IIA activity trial of TKI258 for treatment of castrate resistant prostate cancer with skeletal metastases. The two primary outcomes are survival time and early response as characterized by a drop in PSA as defined by working group criteria (25).

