Historical Experience and Goals: Based on the historical experience in which the mean survival time was 8 months, under a Bayesian model we assume that the unadjusted mean survival time with TKI258 follows an uninformative inverse gamma with mean 8 and variance 1000, equivalently with scale parameter 2.064 and shape parameter 8.512, denoted mE ~ IG(2.064, 8.512). A mean survival time on average > 10 months would be considered promising evidence of anti-disease activity. Formally, assuming that the historical mean survival mH ~ IG(52, 400), TKI258 will be considered promising if, based on the data from the trial, Pr(mE > mH | data) > .95. The planned sample size is 40 patients, with an anticipated accrual rate of 3 patients per month. In addition, the relationships between several potential prognostic covariates and the above clinical outcomes will be explored, as described below.

Monitoring Rules: No early stopping rule in terms of the probability of PSA response will be employed because it is not known whether blocking the stromal-epithelial interactive pathway (SE-pathway) will be related to clinical benefit. Consequently, it may be the case that PSA does not drop but survival time is prolonged due to inhibition of disease progression by TKI258. Given the short survival time of these patients and anticipated accrual rate of 3 patients per month, it will not be feasible to implement an early stopping rule in terms of observed survival times. However, based on an historical rate of 20% grade 3 or 4 toxicity with standard therapies, it will be assumed that p = Prob(grade 3 or 4 with TKI258) follows a beta prior with parameters (.20, .80). Using the method of Thall and Suung (26), based on the observed toxicity data, accrual to the trial will be stopped early if Pr(p > .20 | data) > .95, with this rule applied after successive cohorts f size 5. This rule says to stop the trial if [# patients with a grade 3 or 4 toxicity]/[# patients evaluated] is greater than or equal to 3/5, 5/10, 7/15, 8/20, 9/25, 11/30, 12/35. The operating characteristics of this rule are summarized in the following table.

True Prob(toxicity)	Prob(Stop Early)	Achieved Sample Size
		$25^{\text{th}}, 50^{\text{th}}, 75^{\text{th}}$ percentiles

.10	.01	40 40 40
.20	.11	40 40 40
.30	.47	20 40 40
.40	.86	5 15 25

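### Section 10 reduces the NTX and bone alkaline phosphatase changes to undefined binary indicators and names no analysis on the measured scale, although one primary-objective bullet correlates marker change with PSA.

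*Combined protocol and SAP*

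**What the plan says.** Section 2.1 has two bullets under the primary objective. The first is to estimate overall survival and early PSA response. The second is to identify PSA modulation in 40 patients and "to correlate PSA Modulation with changes in bone remodeling markers".

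Section 10 gives the analysis: "The effects of the following four potential prognostic covariates on Prob(PSA response) will be estimated using logistic regression", with a Cox or alternative model for survival. It then states "Each of the following covariates is a binary indicator" and lists, as item 2, "Modulation of the bone markers (a) urinary NTX and (b) bone specific alkaline phosphatase". No section says how large a change counts as modulation, in which direction, or at which visit.

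The markers are collected as quantities. Section 7.2 takes both at screening. Section 7.4.3 repeats both from Cycle 1 Day 1 every 4 weeks for the first 8 weeks, then every 8 weeks.

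On size and status, Section 10 says: "The planned sample size is 40 patients, with an anticipated accrual rate of 3 patients per month", and "the relationships between several potential prognostic covariates and the above clinical outcomes will be explored". The two primary outcomes are survival time and PSA response. The rule for calling the drug promising uses survival only.

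**The concern.** Splitting a continuous marker into yes and no treats all patients on one side of the cut as alike. In a single-arm study of 40 patients there is little information to spare.

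Leaving the cut open adds a second problem. A fixed split costs power. A split picked because it separates the outcomes well produces associations that are not there. The plan rules out neither, and the choice arises for two markers and two outcomes.

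The objective asks for a correlation of changes. The only analysis in Section 10 that links marker to PSA relates a yes/no marker to a yes/no PSA response. That gives an odds ratio between two dichotomies.

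**Working it through.** The documents state no power, alpha or effect size for this analysis, so there is no planned figure to reproduce. From the documents: n = 40, binary coding, logistic regression of PSA response. Assumed: a roughly normal marker change, a linear effect and two-sided 5%.

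**1. Information kept after a split.** With a share p on one side of the cut, the relative efficiency is φ(z_p)² / [p(1 − p)].

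- Median split: 0.3989² / 0.25 = 0.637 (that is, 2/π). Loss 36%, like 40 × 0.637 = 25.5 patients.
- 30/70: efficiency 0.576, loss 42%, like 23.0 patients.
- 20/80: 0.2800² / 0.16 = 0.490. Loss 51%, like 19.6 patients.
- 10/90: efficiency 0.342, loss 66%, like 13.7 patients.

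Under this model the median split is the most favourable cut.

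**2. Correlation of marker change with a continuous PSA change.** Approximate power is Φ(atanh(r) × √(n − 3) − 1.96). For a true r of .4:

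- Continuous: atanh(.4) = .424; .424 × 6.083 − 1.96 = .62; power .73.
- Median split: r shrinks to .4 × √.637 = .319; power .52.
- 20/80 cut: r shrinks to .4 × √.490 = .280; power .42.

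Simulation gives .75 against .53 for continuous against median split. At r = .5 it gives .92 against about .75. The correlation detectable with 80% power is .43 on the measured scale. After a median split the underlying correlation must be .43 / .798 = .54.

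**3. The planned model: logistic regression of PSA response.** Simulated likelihood-ratio test, n = 40, log odds ratio 1.0 per SD (odds ratio 2.7), one marker and no other covariates.

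| Assumed PSA response | Continuous | Median split | 70/30 split |
|---|---|---|---|
| 20% | .62 | .43 | .45 |
| 35% | .77 | .59 | .56 |
| 50% | .81 | .62 | .57 |

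At 30% response, the continuous and median-split powers are .74 and .54. Across 20% to 50% response and cuts from 50/50 to 80/20, the loss is about 16 to 31 points.

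**4. A cut chosen from the data.** With no true association, n = 40 and a continuous outcome, taking the best cut between the 20th and 80th percentiles raised the false-positive rate from 5% to 27%. Taking the best of the three quartile cuts gave 12%.

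**5. Who has a week-8 value.** Eight weeks is about 56 / 30.4 = 1.84 months. With exponential survival and the means named in Section 10:

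- Mean 10 months: 1 − exp(−1.84/10) = 17% die before week 8.
- Mean 8 months: 1 − exp(−1.84/8) = 21%.

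That is roughly 7 to 8 of 40 patients, before any other dropout.

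**The case against.** The strongest reply is that the binary rule governs prognostic covariates in models the plan calls exploratory, and that no section says those models answer the second primary-objective bullet. This is correct and limits the weight of the point. It does not remove the point, because Section 10 names no other analysis for that bullet.

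A reader might infer that the trial's main conclusion rests on these indicators. The documents do not support that: the primary outcomes are survival and PSA response, and the promising rule does not use the markers.

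The size is also open to challenge. Every power figure depends on an assumed response rate, effect and cut. The loss shrinks if the true effect is a threshold at the chosen cut. Hence a range is given and not a single number.

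Two further inferences should be resisted.

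- Applying the expected 60% positive-biopsy rate to reach 24 evaluable patients is wrong here. NTX is measured in urine and bone alkaline phosphatase in serum, and their collection does not depend on the biopsy result.
- Stable bisphosphonate use is allowed ("Patients on stable doses of bisphosphonates that show subsequent tumor progression may continue on this medication") and the model has no term for it, but that does not show the association is distorted. Section 4.2 bars starting within 4 weeks before the first dose or during the study, and the documents do not say how many patients are users.

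Finally, extra covariates are not free. At 30% response there are 0.30 × 40 = 12 responders, and the gains above were computed without adjustment terms.

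**Conclusion.** The concern holds as a weakness of analysis that is cheap to correct. Both bone markers enter Section 10 only as binary indicators with no cut-point or time point, and nothing uses their measured change. Given a roughly normal marker and a linear effect, the information lost is about 36% at best and 51% at a 20/80 cut. In the planned logistic model that means about 16 to 31 points of power at an odds ratio of 2.7 per SD, two-sided 5% and 20% to 50% response. It affects one of two primary-objective bullets and the exploratory covariate models. It does not affect the survival decision rule.

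**What to change.** Amend Section 10 as follows.

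- Enter each marker as the continuous log ratio to baseline at one fixed visit (week 8), one marker per model.
- For the second primary-objective bullet, report the correlation (for example Spearman) of PSA change with marker change, with a confidence interval.
- For survival, start the analysis at a week-8 landmark, and state how many patients lack a week-8 value.
- Keep any binary version as a secondary display, with its cut-point fixed in advance.
- Treat adjustment for baseline marker value and baseline bisphosphonate use as a sensitivity analysis, given perhaps only 12 responders.

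The cost is plan wording: no new visits, samples or patients, since the measurements are already scheduled. There are two downsides. Effects are reported per unit of log change and not as yes/no, and the landmark analysis excludes early deaths (about 17% to 21% under the exponential assumption).
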